## Clarifications to Final SAP reflecting Primary Paper in the New England Journal of Medicine 05-15-2021:

- 1. Throughout the protocol and SAP, we refer to the ABC-SW, which is a modified subscale of the ABC-Lethargy, Social Withdrawal Subscale that eliminated questions 3, 32, and 53, which refer to lack of movement, in order to increase specificity for social reciprocity behaviors. In writing the primary paper, we wanted to eliminate any possible confusion with the original published ABC-Lethargy, Social Withdrawal subscale and referred to the modified scale as the ABC-modified Social Withdrawal subscale or ABC-mSW. We have changed our clinicaltrials.gov primary results to use the new nomenclature of ABC-mSW.
- 2. Reviewers pointed out that it was not entirely clear what our three secondary outcomes were. Therefore, we want to be clear that they are:
  - a. the Sociability Factor (abbreviated SF) which combines the ABC-mSW and the PDD-BI screening version in order to assess both areas of social reciprocity challenges and social skills (there was an error in the original version of the final SAP in which the sociability factor was inadvertently omitted from section 4.1.2, which has been corrected)
  - b.the Social Responsiveness Scale, 2nd Edition Social Motivation Subscale (abbreviated SRS-2-SM); c. the Stanford Binet, 5th edition Abbreviated Intelligence Quotient (abbreviated ABIQ).
- 3. Reviewers requested that we clarify what our sensitivity analyses were. They follow
  - a. Analysis using the original ABC-Lethargy, Social Withdrawal Subscale
  - b. Analysis integrating baseline (or screen if no baseline was available) plasma oxytocin level, baseline oxytocin level x treatment, and baseline oxytocin x treatment x time into the MMRM model
  - c. Analysis separately of the ABC-mSW outcome in the minimally verbal and fluently verbal subgroups.
  - d. Analysis of the ABC-mSW outcome in the per proctocol population
- 4. In the primary paper we also clarify that the full analysis set is essentially a modified intent treat sample, and that age group was dropped from the final analysis model because it was not significant.

Initial Statistical Analysis Plan for SOARS-B

Version 1.0

March 21, 2013

Study of Oxytocin in ASD to Improve Reciprocal Social Behaviors (SOARS-B)

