**ABC-SW Total** 

Sociability Factor (SF)

The SF will be calculated by discarding the three lethargy items (3, 32, 53) from the ABC-SW, summing the 13 remaining items of the ABC-SW subscale, and adding the sum to the PDDBI-SV raw social deficits score.

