#### 1.2.2 SECONDARY OBJECTIVES

- To determine the efficacy of OT as measured by changes in ABC-SW scores as a function of baseline plasma oxytocin levels, age and functional level and the interaction of each with treatment, and with treatment and week.
- To determine the safety and tolerability of OT in participants with ASD as measured by incidence of treatment emergent adverse events (TEAEs) and abnormal laboratory values, tolerability of OT dose, and time to early termination.
- To determine the efficacy of OT as measured by changes in the sociability factor (SF), a combined measure formed from 13 items of the ABC-SW and the Pervasive Development Disorders Behavior Inventory –Screening Version (PDDBI-SV).
- To determine the efficacy of OT as measured by changes in ABC-SW scores in low-functioning and highfunctioning strata separately.
- To determine the efficacy of OT as measured by changes in Social Responsiveness Scale Version 2 (SRS-2) Social Motivation scores and Stanford Binet-5 Abbreviated IQ standard scores.

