# **4.1 Efficacy Variables**

Detailed description of all efficacy variables is given in the protocol. All efficacy variables will be analyzed as change from baseline, except where noted.

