## 2.2 Study Outcome Measures

#### 2.2.1 **Primary Outcome Measures**

Our primary outcome is reciprocal social behaviors, which we will assess using two co-primary measures. The first measure is the ABC-SW subscale, which is being used in other clinical trials focusing on the core social and communication symptoms of autism. The other measure is the

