Sociability Factor (SF), a combined measure derived from 13 items of the ABC-SW, which primarily captures aloof, and avoidant behaviors, and the Pervasive Developmental Disorders Behavior Inventory-Screening Version (PDDBI-SV, Cohen 2011), a recently developed measure which assesses both maladaptive social problems and social skills. The PDDBI-SV is comprised of 18 items included in the older, more comprehensive Pervasive Developmental Disorders Behavior Inventory (PDD-BI, Cohen 2003). The PDDBI-SV assesses both social impairments typically associated with the active but odd subtype of ASD and development of pro-social skills that are integral to improved reciprocal social behavior. The PDDBI-SV results in a raw SOCDEF score, which is the sum of the reverse-scored social skills and the regularly-scored problems, and a SOCDEF T score. In marked contrast to the PDD-BI's age-based standard scores (for children 1.5 and 12.5 years old), the PDDBI-SV SOCDEF score does not change with age in individuals with ASD. The PDDBI-SV has been validated in original PDD-BI development sample of 311 children 1-17 years old and a recently-acquired sample that includes 145 youth between 13 and 15 years old, 90 between 16 and 19 years, and 59 between 20 and 40 years (Cohen 2011, personal communication). The sociability factor SF will be calculated by discarding the three lethargy items from the ABC-SW (questions 3, 32, and 53, which all assess reduced physical movement), summing the 13 remaining items of the ABC-SW subscale, and adding it to the PDDBI-SV raw SOCDEF score. The sociability factor SF is derived from two well-validated instruments and has face validity for capturing the full range of impairments in reciprocal social behaviors observed in ASD. We chose not to use the Social Responsiveness Scale (SRS), which was developed to provide a quantitative measure of social impairments typically observed in ASD in children 3-18 years old, because it has been demonstrated to be quite stable over time (Constantino, Przybeck et al. 2000; Constantino 2009) and no intervention studies have clearly demonstrated its sensitivity to change.

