### **10.2** Sample Size Considerations

We will use a mixed longitudinal model for our primary analyses (see Statistical Analyses below). Since some aspects of the model such as covariance structure are unknown, we performed power and sample size calculations using a more conservative, simplified model corresponding to a two-group t-test on change scores. We plan to analyze two co-primary outcome measures: the ABC-SW, which will provide consistency with pivotal trials of other medications hypothesized to improve ASD social symptoms, and the combined social score, which integrates ABC-SW symptoms with the new Pervasive Developmental Disorders Behavior Inventory-Screening Version SOCDEF raw score (PDDBI-SV, Cohen 2011, also see Outcome Measures) in order to fully capture the range of impairments in reciprocal social behaviors observed in ASD. We will use an alpha of 0.025 to correct for two co-primary outcomes. SOARS-B is powered for Aim 1b to allow independent evaluation of oxytocin efficacy in low and high-functioning youth.

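### The 2021 clarification says ABC-SW always meant the subscale without items 3, 32 and 53, but protocol v6.0 and SAP v1.0 say otherwise, SAP v2.0 names no items, and the 13-item primary is undated

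*Combined protocol and SAP*

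**What the plan says.** **Clarifications page (05-15-2021).** Item 1 says "Throughout the protocol and SAP, we refer to the ABC-SW, which is a modified subscale of the ABC-Lethargy, Social Withdrawal Subscale" and explains that questions 3, 32 and 53 were dropped. It presents the newer label, ABC-mSW, as a change of name. Item 3a lists as a sensitivity analysis "Analysis using the original ABC-Lethargy, Social Withdrawal Subscale".

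**Protocol v6.0, section 2.2.1.** The first co-primary is introduced thus: "The first measure is the ABC-SW subscale, which is being used in other clinical trials". The second, the Sociability Factor (SF), is built by "discarding the three lethargy items from the ABC-SW (questions 3, 32, and 53, which all assess reduced physical movement), summing the 13 remaining items" and adding the PDDBI-SV raw score. Section 10.2 justifies the choice of "the ABC-SW, which will provide consistency with pivotal trials of other medications hypothesized to improve ASD social symptoms".

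**SAP v1.0, Primary Efficacy Variables.** ABC-SW Total and the SF are listed as separate co-primaries: "The SF will be calculated by discarding the three lethargy items (3, 32, 53) from the ABC-SW, summing the 13 remaining items".

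**SAP v2.0.** Section 1.2.2 describes the SF as "a combined measure formed from 13 items of the ABC-SW" plus the PDDBI-SV. Section 4.1.1 names the ABC-SW score as primary without listing items, and section 4.1 says "Detailed description of all efficacy variables is given in the protocol". Section 4.4 plans one sensitivity analysis, in the per-protocol population.

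**Planning figures.** SAP v2.0 section 6 and protocol v6.0 section 10.2 both use an SD of 9, a difference of 5, a meaningful difference of 5-7 points, and 71 per treatment group in each of two strata (284 in total). The SAP attaches 90% power at alpha 0.05 to the 71; the protocol attaches 80% at alpha 0.025.

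**The concern.** The item set is the most basic part of a primary endpoint's definition. Someone who takes SAP v2.0 section 4.1.1, follows the reference to the protocol and scores the ABC-SW as described there obtains a different primary score from the one the clarification names. The clarification says there was never a difference, and the text does not bear that out.

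Two things are at stake. First, with two versions of the score available and no date for the choice between them, the documents alone do not let a reader confirm that it was made blind. Second, the SD, the target difference and the 5-7 point threshold were carried through unchanged. Nothing says whether they describe the 13-item score, so a reported difference on that score has no stated benchmark.

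**Working it through.** **Step 1: which items does ABC-SW contain in each document?**

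| Document | Treatment of items 3, 32, 53 | Reading of ABC-SW |
|---|---|---|
| Protocol v6.0, 2.2.1 | Taken out of the ABC-SW, for the SF only; 13 left | Explicit: 13 + 3 = 16 items (derived; 16 is not printed) |
| SAP v1.0, Primary Efficacy Variables | Same | Explicit: same |
| SAP v2.0, 1.2.2, 4.1, 4.1.1 | Not mentioned; definitions referred to the protocol | By implication: unmodified score |
| Clarification 1 (2021) | Already excluded | 13 items |

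A score from which three items have still to be removed cannot already lack them.

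**Step 2: is a change recorded?** The 24-item summary of SAP changes covers dropping the SF as a primary, and at items 5, 8 and 22 it admits errors in the final SAP or its figure. It says nothing about the primary's items. The protocol summaries record the dropped co-primary but no change of item set. The original-subscale sensitivity analysis is in clarification 3a, not in SAP v2.0 section 4.4. Within these documents the 13-item primary is first explicit on the 2021 page.

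**Step 3: reproduce the sample size.** Two-sided two-sample t-test, standardised difference 5/9 = 0.556.

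- 90% power at alpha 0.05 needs 69.1, so 70 per group; 71 gives 90.8%. The SAP v2.0 statement reproduces.
- 71 × 4 = 284; 284/0.95 = 299 and 284/0.99 = 287, close to the stated 300 and 290.
- 80% power at alpha 0.025 needs 62.9, so 63 per group; 71 gives 85.1%. The protocol's 80% does not reproduce.

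**Step 4: what could 13 items do to power?** The documents give no 13-item SD or difference, so these are assumptions. If item changes have equal variance and common correlation r, the 13-item SD is 9 × √[(13 + 156r)/(16 + 240r)]. At r = 0 this is 9 × √(13/16) = 8.11; at r = 1 it is 9 × 13/16 = 7.31. The difference either stays at 5 or scales to 5 × 13/16 = 4.06. I add the case in which only the difference shrinks. Alpha is 0.05 throughout.

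| Difference | SD | Power, 71 per group (one stratum) | Power, 142 per group (whole sample) |
|---|---|---|---|
| 4.06 | 9 | 76% | 97% |
| 4.06 | 8.11 | 84% | 98.8% |
| 4.06 | 7.31 | 91% | 99.7% |
| 5 | 8.11 | 95% | 99.9% |
| 5 | 7.31 | 98% | >99.9% |

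If the difference and SD shrink in proportion, power does not change. If the 5-7 point threshold scaled with item count it would be 4.1-5.7.

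**The case against.** The clarification is headed as applying to the final SAP, so its word SAP most naturally means v2.0, and v1.0 is superseded. SAP v2.0 never says the three items are removed from anything. Its phrase about 13 items does not prove that its ABC-SW had more than 13, since a 13-item scale also contributes 13 items. This stands: for v2.0 the unmodified reading rests on the reference to the protocol and is an implication only. It does not rescue the clarification, which also covers the protocol, and protocol v6.0 section 2.2.1 is explicit.

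A reader might infer that the 13-item score was picked after the results were known, because it first appears in 2021. The documents do not support that. They present a change of label, give no date for the choice, and mention a registry entry that is not part of this material. Only a request for the date is justified.

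A reader might also infer that the trial was underpowered for the 13-item score. That does not follow either. The range comes from assumed scalings and runs in both directions. Nor do the documents say which items the trials behind the SD of 9 scored.

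Finally, much is already disclosed: the 2021 page states the item set and lists the original-subscale analysis. That is true, and it is why the remedy is small. The protocol power line is a separate matter and errs on the safe side, but the figure is still wrong as printed.

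**Conclusion.** The point holds as a documentation error about the primary endpoint and should be fixed. The clarification's sentence contradicts protocol v6.0 section 2.2.1 and SAP v1.0 explicitly, and SAP v2.0 by implication. The move to a 13-item primary is neither recorded nor dated, and the planning figures are not tied to a score.

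The numerical consequence is unknown. Under the scalings in the working, power per stratum runs from about 76% to 98% and stays at about 97% or more for the primary comparison in all participants. The low end requires the difference to shrink while the SD stays at 9, which is above the 8.11 maximum under equal item variances and non-negative correlations. N is not shown to be wrong, and no bias in the choice of score is shown.

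Separately, 71 per group per stratum gives about 85% power at two-sided alpha 0.025, not the 80% in protocol section 10.2. The error is conservative.

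**What to change.** On the clarifications page, leaving the 2018 SAP text as it is:

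1. Replace the claim about the protocol and SAP with a statement that protocol section 2.2.1 and SAP v1.0 describe the ABC-SW before items 3, 32 and 53 are removed, and that SAP v2.0 section 4.1.1 did not name the items.
2. State the 13-item set as the primary, with the date or document version of that decision and whether it preceded unblinding.
3. Report the 13-item and original-subscale results side by side.
4. Say which score the SD of 9, the difference of 5 and the 5-7 point threshold refer to.
5. Note that the protocol section 10.2 power figure should read about 85% at two-sided alpha 0.025 with 71 per group per stratum (63 would give 80%).

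The cost is a few sentences and one date. Both scores are already listed for analysis, so no new data or analyses are needed. The price is an openly stated difference between the protocol text and the reported primary score.

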# LIST OF ABBREVIATIONS

Abbreviation or	Explanation
term	
ABC	Aberrant Behavior Checklist
ABC-SW	Aberrant Behavior Checklist – Social Withdrawal subscale
ADI-R	Autism Diagnostic Interview - Revised
ADOS-2	Autism Diagnostic Observation Schedule (version 2)
AE	Adverse Event
ALT	Alanine Aminotransferase
ASD	Autism Spectrum Disorder
AST	Aspartate Aminotransferase
BMI	Body Mass Index
BUN	Blood Urea Nitrogen
CASI	Childhood Anxiety Symptom Inventory
CGI-I	Clinician Global Impression - Improvement
CGI-S	Clinician Global Impression - Severity
CI	Confidence Interval
cl	Chloride
CO2	Carbon Dioxide
CSQ	Caregiver Strain Questionnaire
CSS	Calibrated SeverityScore calculated from the ADOS-2
DSM-V	Diagnostic and Statistical Manual of Mental Disorders, Fifth Edition
DSMB	Data Safety Monitoring Board
ECG	Electrocardiogram
GUID	Global Unique Identifier
FAP	Full Analysis Population
IU	International Unit
K	Potassium
LS	Least Squares
OT	(intranasal) Oxytocin
M0	Month 0 Visit
M6	Month 6 Visit
M12	Month 12 Visit
M18	Month 18 Visit
MMRM	Mixed Model with Repeated Measures
mRNA	Messenger Ribonucleic Acid
Na	Sodium
NIH	National Institutes of Health
PDDBI-SV	Pervasive Developmental Disorders Behavior Inventory – Screening
	Version
PDDBI-Full	Pervasive Developmental Disorders Behavior Inventory – Full Version
PP	Per-protocol Population
OXTR	Human Oxytocin Receptor Gene
Q1	First Quartile
Q3	Third Quartile
QTcB	QT interval corrected for heart rate using Bazett's formula

Abbreviation or	Explanation
term	
QTcF	QT interval corrected for heart rate using Fridericia's formula
RMET	Reading the Mind in the Eyes Test
SAP	Statistical Analysis Plan
SD	Standard Deviation
SF	Sociability Factor, a combined measure derived from the ABC-SW & PDDBI-SV
SLAES	Systematic Longitudinal Adverse Events Scale
SOARS-B	Study of Oxytocin in ASD to Improve Reciprocal Social Behaviors
SRS-2	Social Responsiveness Scale (version 2)
TEAE	Treatment-Emergent Adverse Event

#### **INTRODUCTION**

## **Purpose**

The purpose of this SAP is to outline the planned analyses to support the completion of the primary manuscripts to be written for the SOARS-B Study. Exploratory analyses not identified or defined in this SAP may be performed to support the clinical trial. Any post-hoc or unplanned analyses performed and not identified in this SAP will be documented in the respective manuscript.

# **Study Objectives**

# **Primary Objective**

To determine the efficacy of intranasal oxytocin (OT) for the treatment of deficits of reciprocal social behaviors in child or adolescent participants with autism spectrum disorders (ASD) as measured by changes in the Aberrant Behavior Checklist- Social Withdrawal Scale (ABC-SW) and the sociability factor (SF), a combined measure formed from 13 items of the ABC-SW and the Pervasive Developmental Disorders Behavior Inventory - Screening Version (PDDBI-SV).

## **Secondary Objectives**

To determine the safety and tolerability of OT in participants with ASD as measured by incidence of treatment emergent adverse events (TEAEs) and abnormal laboratory values, tolerability of OT dose, and time to early termination.

To determine the efficacy of OT as measured by changes in ABC-SW and SF scores in low-functioning and high-functioning strata separately.

To determine the efficacy of OT as measured by changes in Social Responsiveness Scale Version 2 (SRS-2) Social Motivation scores, Vineland 2 Adaptive Behavior Composite score and Nonverbal IQ or Mullen Early Learning Composite scores.

To determine the efficacy of OT (as measured by changes in ABC-SW scores, SF scores, SRS-2 Social Motivation scores, Vineland 2 Adaptive Behavior Composite, and Nonverbal IQ or Mullen Early Learning Composite scores) as a function of age.

To determine the efficacy of OT (as measured by changes in ABC-SW scores, SF, , SRS Social Motivation scores, Vineland 2 Adaptive Behavior Composite , and Nonverbal IQ or Mullen Early Learning Composite scores) as a function of baseline percent *OXTR* gene methylation.

# **Exploratory Objectives**

To describe the influence of OT on the oxytocin system as measured by changes in *OXTR* gene methylation, mRNA expression of oxytocin relevant genes, levels of oxytocin in plasma and saliva, and whole blood serotonin levels over time.

To determine the efficacy of OT on other clinical assessments including the subscales of the ABC, SRS, Vineland, and PDDBI; the ADOS Calibrated Severity Score (CSS); the Clinical Global Impressions Severity and Improvement scores; self-reported social functioning and the Reading the Mind in the Eyes Task (RMET).

To examine the potential interaction between OT and various types of concurrent behavioral and/or

pharmacological treatments and social opportunities.

[figure not shown]
# Study Design

This is a multicenter, randomized, double-blind, stratified, flexible dose, placebo-controlled study designed to evaluate OT in participants with ASD. OT will be given as an intranasal preparation with two different concentrations of 8 IU per insufflation or 24 IU per insufflation. Oxytocin will be administered daily, in single doses up to 40IU or divided doses in the morning and early afternoon as described in the protocol. Total daily dose is flexible, between 8 IU and 80 IU per day.

Participants who successfully complete screening and baseline assessments and are deemed eligible will be randomized to OT or placebo treatment in a 1:1 ratio, stratified by age group (3-6, 7-11, 12-17) and functioning (low, high), for a total of 6 strata. Randomization will not be stratified by center, as it was felt that additional stratification by center would lead to too many strata, a loss of degrees of freedom, and the potential for a grossly unequal randomization to treatments.

A schematic representation of the study design is shown in Figure 1. After screening and randomization at month 0 (M0), participants enter a double-blind treatment period of 6 months (M6), followed by open-label treatment with OT for 6 months, termination of OT at the end of month 12 (M12), and an 18 month (M18) follow-up visit 6 months after the month 12 visit.

Efficacy, safety, and tolerability are measured monthly throughout the treatment period. Participants who terminate early will be asked to provide safety data through the remainder of the study. The schedule of assessments is provided in Table 1.

Schematic Representation of the Study Design Figure 1:

nle taken Primani nutcome aggi

Table 1: Schedule of Visits and Assessments

Table 1: Sched	lule of Visi	ts and P	155625	ments	•											Post
SCHEDULE OF EVENTS	Screen		Dou	ble Bl	ind Tr	eatm	ent				Op	en Tr	eatme	ent		Tx f/u
Procedure	1 or 2	M 0.5	M1	M2	М3	M4	M5	M6/ T	M 6.5	M7	M8	M9	M10	M11	M12/ T	M 18
ADOS-2	Х							X							Х	
ADI-R	Х															
Stanford Binet/Mullen	Х							Х							Х	Х
DSM-V Checklist	Х															
Inclusion/Exclusion	Х															
Demographics																
Family Med History (NIH	х															
Form)	^															
Randomization Form																
GUID Acquisition Form																
GUID Record Form																
Con Meds	Х		Χ	Х	Х	Х	Х	Х		Χ	Х	Х	Х	Х	Х	Х
Vital Signs	Х		Χ	Х	Х	Х	Х	Х		Χ	Х	Х	Х	Х	Х	Х
Med/Psych History	V	Ī														
(SLAES)	X															
Adverse Effects			V			V	V	\ \ \		V		V	V	V	V	V
(SLAES/Suicidality)			Х	Х	X	X	Х	X		Χ	Х	Х	X	Х	Х	Х
Physical Exam (NIH Form)	Х		Х	Х	Х	Х	Х	Х		Χ	Х	Х	Х	Х	Х	Х
Medical History (NIH	V															
Form)	X															
CGI S and I 			Χ	Х	Х	Х	Х	Х		Χ	Х	Х	Х	Х	Х	Х
Social Skills Therapies			Χ	Х	Х	Х	Χ	Х		Χ	Х	Х	Х	Х	Х	Х
Psychosocial Therapies			Χ	Х	Х	Х	Х	Х		Χ	Х	Х	Х	Х	Х	Х
Laboratory										15 - 27						
ECG	Х							Х							Х	
Female Reproductive	V		V					\ \ \ \ \ \ \ \ \ \ \ \ \ \ \ \ \ \ \		V	\ 	, ,	\ \ \	\ \ \		
Status	X		X	X	X	X	Х	X		Χ	Х	Х	X	Х	X	X
Urine/Serum Pregnancy 	Х															
Safety labs 	Х							Х							Х	
mRNA sample	Х	Ī						Х							Х	
Methylation sample	Х			Х				Х			Х				Х	Х
Plasma/salivary oxytocin	Х			Х				Х			Х				Х	Х
Whole blood serotonin	Х			Х				Х								
Genetic repository																
sample-subj 				Х												
Genetic repository –																
parents 				Х												
Parent Questionnaires																
Questionnaire Guidance			V	Х	V	V	V	Х		V	V	V	V	V	V	V
Form			Х		Х	Х	Х			Χ	Х	Х	Х	Х	Х	Х

			_			_					_	_				
Social Opportunity			X	X	Ιχ	Ιχ	X	X		Х	Х	X	X	X	l x l	X
Questionnaire			_^_	^	_^_	_ ^		^		_^	^	_^_	_^_	^		_^_
ABC				Χ		Χ		Х			Χ		Χ		Χ	Χ
PDDBI-SV				Χ		Х					Χ		Х			
PDDBI-Full								Х							Χ	Х
CASI								Х							Х	Х
Caregiver Strain								Х							Χ	Х
Vineland-II (Survey Form)					Х			Х				Х			Χ	Χ
SRS-2					Х			Х				Χ			Χ	Х
Subject Completed																
Questionnaires	_															
Reading Mind in Eyes Test 				Х				Х			Х				Х	Х
Self-Rating of social								X							Х	Х
function								_ ^							_ ^	^
Medication																
DVD training (med																
administration)*																
Med Administration																
Form*																
Dosing Guide 		X	Χ	Χ	Х	Х	Х	Χ	Х	Χ	Χ	Х	Х	Х		
Risks Handout								Х								
Medication Compliance 			Х	Χ	Х	Х	Х	Х		Χ	Χ	Х	Х	Х	Х	
Oxytocin Dosing Log (staff)		Х	Χ	Χ	Χ	Χ	Х	Х	Х	Χ	Χ	Х	Χ	Χ	Х	
Medication Diary			v	Х	Х	v	Х	Х		Х		V	Х	Х		
Dispensed			Х			Х		^			Х	Х		^_		

0-CGI-S only at baseline, CGI-S and I at all other visits 1-Required at screening but can be done at any time during the course of the study at physician discretion 2-Safety labs to include: glucose (random), CO2, CI, K, Na, Creatinine, BUN, AST, ALT, urine specific gravity, urine pregnancy in pubertal girls. 3- Preferred time to collect, but can be done at any time. 4- One sample is requested from each biological parent, can be obtained at any point during the study 5- Assessment will be obtained only in participants who have fluent phrase speech & can define basic feelings and friendship. 6-. Completed each time the participant returns study medication 7- Dosing guide should be given at each visit (and also phone calls where the dosing has changed). Staff will circle the appropriate column for dosing that the patient should follow

\*Must be given at baseline, but also can be given at any other time during the course of the study at study staff discretion

